
 To determine parent GSK3640254 and total drug-related radioactivity systemic concentrations following a single IV microtracer dose of [¹⁴C]-GSK3640254 (with an oral dose of non-radiolabelled GSK3640254) and oral dose of [¹⁴C]-GSK3640254¹ 	
 AUC(0–inf), AUC(0–t), C_{max}, t_{max} and t_{1/2} of parent and total drug-related material (radioactivity) in plasma and blood. Volume of distribution at steady state (V_{ss}) and clearance (CL) of parent after IV dose (Period 1 only). Renal clearance of parent (CL_r) after both IV and oral dose Oral clearance (CL/F) and apparent volume of distribution (V_z/F) for the parent following oral administration

 To calculate the absolute oral bioavailability of GSK3640254 	
 Direct estimation of absolute oral bioavailability (F), indirect calculation of fraction of drug escaping first pass hepatic clearance (F_h), fraction absorbed (F_a) and fraction of drug escaping gut metabolism (F_g).

 To determine the rate and extent of excretion of total radioactivity in urine and feces and the total recovery of radioactivity, following IV and oral administrations of [¹⁴C]-GSK3640254 	
 Urinary and fecal cumulative excretion as a percentage of the total radioactive dose
Secondary	

 To evaluate the safety and tolerability of GSK3640254 after single IV and oral doses in healthy participants. 	
 Characterize observed adverse events, and abnormal laboratory, 12-lead ECG, and vital signs assessments observed.

 To determine the blood:plasma ratio of [¹⁴C]-GSK3640254-related materials (total radioactivity) associated with blood cellular components 	
 Blood:plasma ratio of [¹⁴C]-GSK3640254-related materials (total radioactivity).
Exploratory	

 To generate samples that will be used to characterize the metabolite profile of GSK3640254 following a single IV microtracer dose of [¹⁴C]-GSK3640254 	
 Characterization and quantification of metabolites in plasma, urine, feces, and duodenal bile (qualitative identification in bile). These analytical investigations will be

Objectives	Endpoints ¹

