3. OBJECTIVES AND ENDPOINTS

Objectives	Endpoints
Primary	

 To determine parent GSK3640254 and total drug-related radioactivity systemic concentrations following a single IV microtracer dose of [14C]-GSK3640254 (with an oral dose of non-radiolabelled GSK3640254) and oral dose of [14C]-GSK3640254¹ 	
 AUC(0–inf), AUC(0–t), Cmax, tmax and t1/2 of parent and total drug-related material (radioactivity) in plasma and blood. Volume of distribution at steady state (Vss) and clearance (CL) of parent after IV dose (Period 1 only). Renal clearance of parent (CLr) after both IV and oral dose Oral clearance (CL/F) and apparent volume of distribution (Vz/F) for the parent following oral administration

 To calculate the absolute oral bioavailability of GSK3640254 	
 Direct estimation of absolute oral bioavailability (F), indirect calculation of fraction of drug escaping first pass hepatic clearance (Fh), fraction absorbed (Fa) and fraction of drug escaping gut metabolism (Fg)

 To determine the rate and extent of excretion of total radioactivity in urine and feces and the total recovery of radioactivity, following IV and oral administration of [14C]-GSK3640254 	
 Urinary and fecal cumulative excretion as a percentage of the total radioactive dose
Secondary	

 To evaluate the safety and tolerability of GSK3640254 after single IV and oral doses in healthy participants. 	
 Characterize observed adverse events, and abnormal laboratory, 12-lead ECG, and vital signs assessments observed.

 To determine the blood:plasma ratio of [14C]-GSK3640254-related materials (total radioactivity) associated with blood cellular components 	
 Blood:plasma ratio of [14C]-GSK3640254-related materials (total radioactivity)

Exploratory	

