8.5.2. Urine Sample Collection

Urine samples will be collected over the time periods specified in the [SoA](#). Urine samples will be used to determine total radioactivity excreted in urine and for subsequent metabolite profiling (to be analysed under a separate protocol).

All participants will be asked to void their bladders before study intervention administration. A blank (pre-dose) urine sample will be collected pre-dose (up to 3.5 h before oral dosing) in Treatment Periods 1 and 2. After oral dosing, in each Treatment Period, urine will be collected over 24 h collection periods as follows: 0-24 h, 24-48 h, 48 – 72 h, 72 – 96 h, 96 – 120 h, 120-144 h, 144-168 h. Further details of urine sample collection, processing, storage and shipping procedures are provided in the SRM.

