5.2.1.2. Derived Pharmacokinetic Parameters**5.2.1.2.1. Derived plasma pharmacokinetic parameters**

PK Parameters will be calculated by standard non-compartmental analysis according to current working practices and using the currently supported version of WinNonlin version 6.3 or above. All calculations of non-compartmental parameters will be based on actual sampling times. PK parameters listed will be determined from plasma GSK3640254, [¹⁴C]-GSK3640254, total radioactivity as data permits and unless otherwise stated.

Table 4 Derived Pharmacokinetic Plasma Parameters

Parameter	Parameter Description
AUC(0-t)	Area under the concentration-time curve from time zero to the time of the last quantifiable concentration (C(t)) will be calculated using the linear trapezoidal rule for each incremental trapezoid and the log trapezoidal rule for each decremental trapezoid.
λ_z	The first order rate constant associated with the terminal (log-linear) portion of the concentration-time curve.
AUC(0- ∞)	Area under the concentration-time curve extrapolated to infinity will be calculated as: $AUC(0 - \infty) = AUC(0 - t) + \frac{C(t)}{\lambda_z}$
%AUCex	The percentage of AUC (0- ∞) obtained by extrapolation (%AUCex) will be calculated as: $\frac{[AUC(0 - \infty) - AUC(0 - t)]}{AUC(0 - \infty)} * 100$
Cmax	Maximum observed concentration, determined directly from the concentration-time data.
tmax	Time to reach Cmax, determined directly from the concentration-time data.
t _{1/2}	Apparent terminal half-life will be calculated as: $t_{1/2} = \ln 2 / \lambda_z$
CL	Total clearance calculated as: $CL = \frac{Dose(IV)}{AUC(0 - \infty)}$ Treatment Period 1, analyte [¹⁴ C]-GSK3640254 only and where the Dose(IV) is the actual IV dose provided by Covance, Harrogate
Vss	Volume of distribution at steady-state, calculated as:

Parameter	Parameter Description
	$V_{ss} = CL * MRT_{iv}$ 
Where CL is total clearance and MRT is the mean residence time, calculated as AUMC(0-∞) [Area under the first moment curve]/AUC(0-∞)

CLr	
If plasma AUC(0-∞) is calculable, then
 $CLr = \frac{\text{Cumulative Ae[Urine] for Period 1}}{\text{Plasma AUC}(0 - \infty)}$ 
If plasma AUC(0-∞) is not calculable, then
 $CLr = \frac{\text{Cumulative Ae[Urine] for Period 1}}{\text{Plasma AUC}(0 - t)}$ 
Where cumulative urine Ae from excretion data for treatment Period 1 and AUC from NCA PK analysis of Treatment Period 1, analyte [¹⁴C]-GSK3640254 only

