ML(iv)	
Metabolite load following intravenous administration, calculated as:
 $ML(iv) = \frac{[\text{Total Radioactivity AUC}(0 - \infty) - [^{14}\text{C}]GSK3640254 \text{ AUC}(0 - \infty)]}{\text{Total Radioactivity AUC}(0 - \infty)}$ 
Treatment Period 1

ML(po)	
Metabolite load following oral administration, calculated as:
 $ML(po) = \frac{[\text{Total Radioactivity AUC}(0 - \infty) - GSK3640254 \text{ AUC}(0 - \infty)]}{\text{Total Radioactivity AUC}(0 - \infty)}$ 
Treatment Period 2
 
Note: GSK3640254 AUC(0-∞) may be updated depending on the sample analysis conducted but refers to the parent GSK3640254 from oral dose

Fg	
Fraction metabolized by gut wall as a fraction of the oral dose, calculated as:
 $Fg = 1 - [ML(po) - ML(iv)]$

CONFIDENTIAL

Statistical Analysis Plan 213051

Parameter	Parameter Description
$CL_{h,iv,blood}$	
Hepatic blood clearance, calculated as:
 $CL_{h,iv,blood} = CL_{h,iv,plasma} * \text{blood to plasma ratio}$ 
Where $CL_{h,iv,plasma}$ is the hepatic plasma clearance calculated as:
 $CL_{h,iv,plasma} = CL - CL_r$
E_h	
Hepatic extraction ratio, calculated as:
 $E_H = CL_{h,iv,blood} / Q_h$ 
Where Q_h = hepatic blood flow (literature value of 1660 mL/min, Edginton, 2006)
 
Note: if assumption that hepatic CL accounts for 100% of the clearance (i.e. CL_r is negligible), then $E_h = CL * \text{blood to plasma ratio} * Q_h$

F_h	$F_h = 1 - E_h$
F_a	
Fraction absorbed following an oral dose, calculated as follows
 $F_a = \frac{F(0 - \infty)] / (1 - E_H)}{F_g}$
Dose(iv)	Radiometric IV dose calculated by Covance
Dose(oral)	Radiometric oral dose calculated by Covance
$F(0-\infty)$	
Oral absolute bioavailability based on $AUC(0-\infty)$, calculated as:
 $F(0 - \infty) = \frac{GSK3640254 \text{ AUC}(0 - \infty)(\text{oral})}{\text{Dose}(\text{oral}) \frac{\text{Dose}(\text{iv})}{[14C]GSK3640254 \text{ AUC}(0 - \infty)(\text{iv})}}$ 
Per Subject

CONFIDENTIAL

Statistical Analysis Plan 213051

Parameter	Parameter Description
	Note: Radiometric dose will be used for IV. GSK3640254 AUC(0-∞) (Oral) refers to the parent GSK3640254 from oral dose, but may be updated depending on the sample analysis

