- Lambda_z is the terminal phase rate constant
- The following PK parameters AUC(0-∞), AUC(0-t), %AUC_{ex}, Cmax, t_{max}, t_{1/2}, CL, V_{dss}, V_z/F and CL/F, will be derived in Phoenix and sent to S&P. The radiometric IV and oral doses will be calculated by Covance and sent to S&P. Additional parameters will be derived by S&P including CL_r, ML(iv), ML(po), F_g, E_h, F_h Fa, F(0-∞), F(0-t) and the [¹⁴C]-GSK3640254/total radioactivity ratios.

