5.2.1.2.2. Derived urine and fecal pharmacokinetic parameters

- Derivation of urine and faecal radioactivity parameters will be the responsibility, or under the direct auspices, of the DMPK department within GSK.
- When summarizing urine and faecal parameters, 'NS' (i.e., no sample provided as subject not voided at particular collection period) or 'NQ' values for these parameters will be imputed with zero.

Table 5 Derived urine and faeces pharmacokinetic parameters

Parameter	Parameter Description
Ae[urine]	Total radioactivity recovered in the urine (Ae[urine]) calculated for each collection interval per subject and treatment period as: Ae[urine]= (concentration in urine sample x collected sample weight) for each urine collection interval, eg 0-24, 24-48, etc.
Cumulative Ae[urine]	Cumulative total radioactivity recovered in the urine (Cumulative Ae[urine]) calculated for each cumulative collection interval per subject and treatment period as: Cumulative Ae[urine] = summation of Ae[urine] For each urine collection with the cumulative urine collection interval
Fe%[urine]	% of total dose excreted as total radioactivity (Fe%[urine]) for each collection interval per subject and treatment period, estimated as: Fe%[urine]=(Ae[urine] for each collection period)/Dose*100. Where the dose is the radiolabelled [¹⁴ C]-GSK3640254, that is in period 1 radiometric iv dose, in period 2 radiometric oral dose
Cumulative Fe%[urine]	Cumulative % of total dose excreted as total radioactivity (Cumulative Fe%[urine]) for each cumulative collection interval per subject and treatment period, estimated as: Cumulative Fe%[urine]= summation of Fe[urine] Where the dose is the radiolabelled [¹⁴ C]-GSK3640254, that is in period 1 radiometric iv dose, in period 2 radiometric oral dose
Ae[faeces]	Total radioactivity recovered in the urine (Ae[faeces]) calculated for each collection interval per subject and treatment period as: Ae[urine]= (concentration in urine sample x collected sample weight) for each urine collection interval, eg 0-24, 24-48, etc.
Cumulative Ae[faeces]	Cumulative total radioactivity recovered in the urine (Cumulative Ae[faeces]) calculated for each cumulative collection interval per subject and treatment period as:

CONFIDENTIAL

Statistical Analysis Plan 213051

Parameter	Parameter Description
	
Cumulative Ae[faeces] = summation of Ae[faeces]
 
For each urine collection with the cumulative urine collection interval

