5.4.1.1. Metabolite profiling analyses in plasma, urine, feces and bile

The metabolic profiling/structural characterization aspect of this work will be performed by GSK (or a GSK representative) in a separate DMPK study report. Data from the quantification of unchanged GSK3640254 in urine following IV administration will be used in the estimate of renal clearance, as detailed above.

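### SAP Table 4 computes renal clearance of parent from total urinary radioactivity, and oral renal clearance is a listed endpoint with no formula

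*SAP*

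**What the plan says.** The endpoint is clearance of parent, by both routes. Protocol section 3 lists "Renal clearance of parent (CLr) after both IV and oral dose" under a primary objective. The Protocol synopsis and SAP 1.2.1, Table 3 (Supplementary 2), 5.2.1 and 5.2.2 carry the same endpoint, and SAP 5.2.2 plans to summarise and list it.

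The derivation is in SAP Table 4 (section 5.2.1.2.1). CLr is cumulative Ae[Urine] for Period 1 over plasma AUC(0-∞), or over AUC(0-t) if the former cannot be calculated. The inputs are "cumulative urine Ae from excretion data for treatment Period 1 and AUC from NCA PK analysis of Treatment Period 1, analyte [¹⁴C]-GSK3640254 only".

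SAP Table 5 defines the numerator: "Cumulative total radioactivity recovered in the urine (Cumulative Ae[urine]) calculated for each cumulative collection interval per subject and treatment period".

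SAP 5.4.1.1 points to a different numerator: "Data from the quantification of unchanged GSK3640254 in urine following IV administration will be used in the estimate of renal clearance, as detailed above".

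Protocol 8.5.2 describes the urine data: "Urine samples will be used to determine total radioactivity excreted in urine and for subsequent metabolite profiling (to be analysed under a separate protocol").

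For hepatic clearance, SAP Table 4 then uses "CL_{h,iv,plasma} = CL - CL_r", which leads on to Eh, Fh and Fa.

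**The concern.** Renal clearance of parent needs parent in both numerator and denominator. The denominator in Table 4 is parent: [¹⁴C]-GSK3640254 in Period 1 is the IV tracer measured by LC+AMS (SAP 5.2). The numerator, taken from Table 5, is all labelled material in urine, including any metabolite. SAP 5.2.1.1 expresses urinary radioactivity as ng equivalents, so the units of the ratio still work and nothing in the output would reveal the mismatch. A programmer following Tables 4 and 5 would report a quantity labelled CLr of parent that is something else, and that quantity then enters CLh, Eh, Fh and Fa.

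The second gap is that CLr after oral dosing is promised in the objectives and the analysis section, yet no formula assigns it a urinary amount or an AUC.

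**Working it through.** The plan states no figure for CLr, so there is nothing to reproduce. The check compares definitions and then sizes the effect.

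**Which urinary amount is defined.** Table 5 defines Ae[urine], cumulative Ae[urine] and the Fe% terms, all as total radioactivity. Neither document defines an amount of unchanged drug in urine. The statement in SAP 5.4.1.1 refers back to an earlier description that does not exist.

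**Error in CLr (IV).** Let p be the share of urinary ¹⁴C that is unchanged parent.

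- Table 4 as written: CLr = Ae(total) / AUC(parent)
- Parent clearance: CLr = p × Ae(total) / AUC(parent)
- Ratio, same AUC, ignoring any truncation of urine collection: 1/p

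| p (assumed) | Table 4 CLr / parent CLr |
|---|---|
| 100% | 1.00 |
| 75% | 1.33 |
| 50% | 2.00 |
| 25% | 4.00 |

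The ratio does not depend on how much label reaches urine. In the AUC(0-∞) branch, CL = Dose(IV)/AUC, so the Table 4 value equals CL × cumulative Fe%[urine]/100. It rescales an excretion result already reported and says nothing specific to parent.

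**Carry-over to Fh and Fa.** Let fe be the fraction of the IV dose recovered in urine as total label, and E = CL × (blood:plasma ratio)/Qh, as the SAP writes it.

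- Fh from Table 4: 1 − E(1 − fe)
- Fh with parent CLr: 1 − E(1 − p·fe)

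Neither fe nor E is given for humans. At assumed p = 50%, the relative change in Fh is:

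| fe (assumed) | E = 0.1 | E = 0.3 | E = 0.5 |
|---|---|---|---|
| 1% | +0.06% | +0.21% | +0.50% |
| 5% | +0.28% | +1.06% | +2.44% |
| 20% | +1.10% | +4.11% | +9.09% |

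Example: fe = 5% and E = 0.5 give 0.525/0.5125 = 1.0244. Since Fa = F/(Fh × Fg), Fa moves the other way. At E = 0.5 it falls by 0.50%, 2.38% and 8.33% for fe of 1%, 5% and 20%.

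**Oral CLr.** Table 4 restricts CLr to Period 1 and the IV tracer. Protocol 9.4.3 derives CLr after IV dosing and only CL/F and Vz/F after oral dosing. SAP 5.4.1.1 also covers IV only. SAP Table 2, which records changes from the protocol analysis, lists only the added Enrolled population.

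**The case against.** The strongest reply is that the intent is plain. The endpoint is named as parent throughout, SAP 5.4.1.1 says unchanged drug will be used, and the closing words of the CLr entry about analyte could be read as covering the urinary amount as well as the AUC. Protocol 8.5.2 is compatible with that, since it sends urine for profiling. On this reading the plan needs only a clarification.

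The intent is indeed clear, but the reading of the analyte phrase is weak. The phrase follows the AUC, the same restriction appears on CL, which uses plasma only, and the urinary amount is said to come from excretion data, which the SAP defines only as radioactivity. Even on the kinder reading, the numerator has no definition.

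The point about carry-over stands. The values of p, fe and E are assumptions, and the SAP itself allows for negligible CLr. The only urinary figure in the documents is 0.04% of total excretion in rats after oral dosing (Protocol Appendix 6). Combined, purely for illustration, with the 15% bioavailability assumed in Protocol 4.3, it gives fe of about 0.04%/0.15 = 0.27%. Fh would then rise by only about 0.015% (E = 0.1) to 0.13% (E = 0.5) at p = 50%. This crosses species and is not a bound, but it suggests that the fe = 20% row is an extreme.

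It also stands that the data-transfer note under Table 4 proves nothing either way. It names no parent amount in urine, but it omits total urinary Ae and the blood:plasma ratio too.

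On oral CLr, the inconsistency does begin inside the Protocol, between its objectives and section 9.4.3. The SAP's general allowance for additional parameters does not supply a formula for an endpoint already promised.

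**Conclusion.** The concern holds on both counts and should be fixed. Followed literally, Tables 4 and 5 give total urinary label over parent AUC, which overstates parent CLr by 1/p: no error if all urinary label is parent, twofold at an assumed 50%, fourfold at 25%. Parent predominance in human plasma (Protocol 4.3) does not settle p in urine. Oral CLr cannot be produced from the formulae given.

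The harm falls mainly on CLr itself, a supplementary estimand under a primary objective in a descriptive study of four to six participants. The effect on Fh and Fa is probably small if urinary excretion is low, and the case does not rest on it.

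**What to change.** For the IV dose, define in Table 4: CLr = cumulative amount of unchanged [¹⁴C]-GSK3640254 in Period 1 urine / plasma [¹⁴C]-GSK3640254 AUC.

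- Give that amount its own symbol, distinct from Ae[urine] in Table 5.
- Source it from the quantification named in SAP 5.4.1.1, and say there that it is labelled drug, because a 200 mg unlabelled tablet is taken in the same period.
- Add it to the inputs in the note under Table 4, and use this CLr in the hepatic clearance step.
- If only total radioactivity is available, do not label the result CLr of parent.
- A minor refinement: if %AUCex, which Table 4 already derives, is material, use an AUC over the urine collection interval.

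For the oral dose there are two options. One is to record in SAP Table 2 that this protocol endpoint will not be derived and remove it from SAP 1.2.1, Table 3, 5.2.1 and 5.2.2. The other is to add a Period 2 formula, if amounts of parent in urine will be available for each participant.

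The cost is SAP wording, and CLr (IV) must wait for profiling data that the SAP already plans to use. Keeping oral CLr would also need parent-in-urine data for Period 2, which SAP 5.4.1.1 does not promise.

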4.3. Justification for Dose

Based on modelling and simulation of virology and PK data, coupled with an ongoing proof of concept (POC) study for GSK3640254 (208132) in HIV-infected participants, the currently projected therapeutic dose range to be investigated in Phase IIb is 50-200 mg once daily. The population PK model of GSK3640254, including parameter uncertainty, was integrated with the PK/Pharmacodynamic (PD) model of GSK3532795 and the distribution of protein binding adjusted (PBA) EC90 values obtained with GSK3640254 from an in vitro experiment with 36 Gag/PR genotyped viruses (e.g. mean of 19.1 ng/mL with CV% of 33%). Further details of the findings in this study are provided in the IB.

The 100 µg microtracer dose administered as a 1 h IV infusion in Treatment period 1 is projected (based on allometry and a conservative assumption of 15% oral bioavailability) to achieve a GSK3640254 C_{max} ~3 ng/mL, which is >200-fold lower than the geometric mean C_{max} following a single 200 mg dose in healthy participants (Study 207187) and >400 fold lower than the geometric mean C_{max} following a single 200 mg dose in HIV-infected patients. This dose can be categorised as a microdose and as such the required safety cover is detailed in International Council for Harmonisation of Technical Requirements for Pharmaceuticals for Human Use (ICH) M3 (R2) ([International Conference on Harmonisation](#), 2009.) In Treatment Period 2, the ¹⁴C labelled solution dose of GSK3640254 is 85 mg (85 uCi) which is partly based on practical limitations and is well within the target dose range to be evaluated in Phase IIb studies.

Preclinical toxicology species provide safety cover for systemic exposure to GSK3640254. Predicted steady-state exposures for a projected 200 mg QD maximum dose in Phase IIb are essentially equal to the no-observed adverse-effect-level (NOAEL) exposure in a 4-week oral toxicity study in rats, although no NOAEL was identified in dogs for GI intolerability and minimal effects of parietal cells following 4 weeks of dosing. However, in this single dose design absorption, distribution, metabolism, and excretion (ADME) study of very limited drug exposure these findings become less relevant.

In vitro studies using hepatocytes from nonclinical species and humans show that there is generally no qualitative difference in metabolites formed. Preliminary non-radiolabelled

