studies showed that GSK3640254 was the predominant drug-related component with low levels of oxidative metabolites in human plasma following repeat oral doses of 320 mg/day (see IB, Section 1.1).

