3. SAMPLE SIZE DETERMINATION

No formal sample size calculation has been performed for this study. However, the sample size reflects an accepted industry standard for human ADME studies using ¹⁴C radiolabelled drug. Additionally, the design of the study in terms of the concomitant administration of intravenous with oral administration (Period 1) inherently reduces variability in the parameters determined, versus a cross-over design for absolute bioavailability assessment, while enabling cross-over to Period 2 in the same participants. The primary objective of the study is to gain a better understanding of the compound's pharmacokinetic, excretory, and metabolic profile and 4 to 6 participants are deemed sufficient for this purpose. Six participants will be enrolled into the study. To minimize the number of participants exposed to radiation; those participants that discontinue early will not be replaced unless the total number of participants who complete both Periods 1 and 2 drops below 4.

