5.2.1. Definition of endpoint(s)

- AUC(0-inf), AUC(0-t), C_{max}, t_{max} and t_{1/2} of parent and total drug-related material (radioactivity) in plasma.
- Volume of distribution at steady-state (V_{ss}) and clearance (CL) of parent after IV dose (Period 1 only)
- Renal clearance of parent (CL_r) after IV and oral administration
- Oral Clearance (CL/F) and apparent volume of distribution (V_z/F) for the parent following oral administration
- Direct evaluation of absolute bioavailability (F), indirect calculation of fraction of drug escaping first pass hepatic clearance (F_h), fraction absorbed (F_a) and fraction of drug escaping gut metabolism (F_g)
- Urinary and fecal cumulative excretion of total radioactivity as a percentage of the total radioactive dose (Period 1 and Period 2)

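### SAP Table 4 labels Fg as the fraction metabolised when the endpoint is the fraction escaping, and its formula has no hepatic term, so the split between Fg and Fa holds only under an assumption the SAP does not state

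*SAP*

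**What the plan says.** The second primary objective is absolute oral bioavailability. Its endpoint consists of F, estimated directly, plus Fh, Fa and Fg, calculated indirectly (Protocol 1.1 and 3; SAP 1.2.1 and 1.2.2). SAP 5.2.1 defines Fg as the "fraction of drug escaping gut metabolism".

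SAP 5.2.1.2.1, Table 4, gives the derivations:

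- ML(iv), "Metabolite load following intravenous administration, calculated as" (AUC of total radioactivity - AUC of labelled parent) / AUC of total radioactivity, Period 1.
- ML(po), "Metabolite load following oral administration, calculated as" the same ratio for the oral dose, Period 2.
- Fg, "Fraction metabolized by gut wall as a fraction of the oral dose, calculated as" 1 - [ML(po) - ML(iv)].
- Hepatic blood clearance: hepatic plasma clearance multiplied by the blood:plasma ratio. Eh is that clearance divided by hepatic blood flow Qh, and Fh = 1 - Eh. A note for the case of negligible renal clearance gives Eh as CL × blood:plasma ratio × Qh.
- Fa, "Fraction absorbed following an oral dose, calculated as follows" [F/(1 - Eh)] / Fg.

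The table states no assumption about hepatic first pass for Fg, and neither document has a rule for Fa above 1. On circulating metabolites, Protocol 4.3 reports from preliminary non-radiolabelled work, after repeat oral doses of 320 mg/day, that "GSK3640254 was the predominant drug-related component with low levels of oxidative metabolites in human plasma".

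**The concern.** There are two separate problems.

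**Label.** A row described as the fraction metabolised feeds an endpoint defined as the fraction escaping. A reader of a table titled from that row would take 0.9 to mean 90% lost in the gut wall, when the formula means 10% lost.

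**Formula.** Subtracting ML(iv) is meant to remove metabolite made after the drug is in the circulation. It does not remove metabolite made when absorbed drug first passes through the liver, which happens after an oral dose and not after an intravenous one. Whatever part of that metabolite reaches plasma raises ML(po) and is read as gut loss. Fa then divides by 1 - Eh as well, so the hepatic loss is taken out twice and Fa is pushed up. In the other direction, a small metabolite signal in plasma holds Fg near 1 whatever the gut does, and the missing drug is booked to Fa as poor absorption.

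Fg and Fa are the primary components meant to explain why bioavailability is what it is. Confusing gut loss, liver loss and poor absorption defeats that purpose.

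**Working it through.** The documents give no numerical Fg, Fa, Fh or metabolite:parent ratio, so there is no planned figure to reproduce. The check puts known true values through the SAP formulas.

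**Step 1, lower bound (no model).** ML(iv) cannot be negative as long as the total radioactivity AUC is at least the parent AUC. Hence Fg = 1 - ML(po) + ML(iv) is at least 1 - ML(po). If the oral metabolite load were 0.10 (illustrative), Fg could not be reported below 0.90, whatever the true gut loss.

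**Step 2, assumed linear model.** Per unit dose, let the IV parent AUC be 1 and the IV metabolite AUC be r. Assume all absorbed drug ends as metabolite, and that metabolite formed in gut and liver reaches plasma equally. Then:

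- oral parent AUC = Fa × Fg × Fh, and oral metabolite AUC = Fa × r
- ML(iv) = r/(1 + r)
- ML(po) = r/(r + Fg × Fh)
- SAP Fg = 1 - ML(po) + ML(iv)
- SAP Fa = Fa × Fg / (SAP Fg), taking Eh as exact

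Only the product Fg × Fh enters the SAP Fg.

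**Step 3, numbers.** True Fa = 1 throughout. Fg, Fh and r are assumptions, with r kept to 0.05 to 0.25 because circulating metabolite is described as low. Example for r = 0.1 and Fg × Fh = 0.5: ML(iv) = 0.1/1.1 = 0.091, ML(po) = 0.1/0.6 = 0.167, and SAP Fg = 1 - 0.167 + 0.091 = 0.924.

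| True Fg, Fh | SAP Fg at r = 0.05 / 0.1 / 0.25 | SAP Fa at r = 0.05 / 0.1 / 0.25 |
|---|---|---|
| 1, 1 | 1 / 1 / 1 | 1 / 1 / 1 |
| 1, 0.9 | 0.995 / 0.991 / 0.983 | 1.005 / 1.009 / 1.018 |
| 1, 0.5 | 0.957 / 0.924 / 0.867 | 1.045 / 1.082 / 1.154 |
| 0.7, 0.7 | 0.955 / 0.921 / 0.862 | 0.733 / 0.760 / 0.812 |
| 0.5, 1 | 0.957 / 0.924 / 0.867 | 0.523 / 0.541 / 0.577 |

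Rows three and five have opposite causes and the same SAP Fg.

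**Step 4, relaxing the equal-appearance assumption.** If only 30% of hepatically formed metabolite reaches plasma, with r now the ratio before that loss, true Fg = 1 and Fh = 0.5 gives Fa = 1.015 / 1.028 / 1.065. True Fg = 0.5 and Fh = 1 gives Fg = 0.954 / 0.914 / 0.824 and Fa = 0.524 / 0.547 / 0.606. The Fa excess shrinks; the understated gut loss largely stays.

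**Step 5, the Eh rows.** SAP 5.3.1.1 defines the blood:plasma ratio as Cb/Cp. The same elimination rate is CL(plasma) × Cp = CL(blood) × Cb, so CL(blood) = CL(plasma) / (Cb/Cp). Table 4 multiplies instead, which scales Eh by (Cb/Cp) squared. For an assumed Cb/Cp of 0.7 and true Eh of 0.5, the SAP Eh is 0.5 × 0.49 = 0.245, and F/(1 - Eh) comes out at (1 - 0.5)/(1 - 0.245) = 0.66 of its correct value.

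**The case against.** A reader might infer that the formula can never tell gut from liver, and that Fg and Fa will therefore come out wrong. The documents do not support that. The non-separability in the table depends on gut and liver metabolite reaching plasma equally. If hepatic metabolite went entirely to bile, and gut metabolite had the same AUC per mole as parent, ML(iv) would be 0. True (Fg = 1, Fh = 0.5) would then give Fg = 1, and true (0.5, 1) would give ML(po) = 0.5/(0.5 + 0.5) = 0.5 and Fg = 0.5, both correct. The protocol plans bile sampling because biliary elimination is an open question. This objection stands against any categorical wording. It does not rescue the formula in general: in that same extreme, true (0.5, 0.5) gives ML(po) = 0.5/(0.5 + 0.25) = 0.667 and Fg = 0.333.

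It is also tempting to quote larger errors, either from r = 1 (Fa = 1.20 at Fh = 0.5) or by treating the "a conservative assumption of 15% oral bioavailability" as all hepatic. The first conflicts with the low metabolite levels the protocol reports. The second reads a planning figure for the IV dose projection as evidence of where drug is lost, which it is not.

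The two harms pull apart: a sizeable Fa excess needs appreciable circulating metabolite, while an Fg held near 1 needs little. The metabolite evidence is itself preliminary and non-radiolabelled, and metabolite load is something this study will measure.

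Finally, the protocol calls these quantities indirect, no hypothesis is tested, the directly estimated F is unaffected, and display conventions sit in an Output and Programming Specification that is not available here. Those points limit the consequence. They do not supply the missing assumption or correct the label.

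**Conclusion.** The Fg label is wrong as written: it contradicts the endpoint definition and the Fa row that uses it. It causes no numerical error.

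The formula is conditionally biased. Fg is overcharged with hepatic loss to the extent that first-pass hepatic metabolite reaches plasma, and Fa then corrects for that loss again. Separately, the bound at 1 - ML(po) means a low metabolite load hides real gut loss and shows it as poor absorption. The direction for Fa is therefore not fixed: too high when loss is mainly hepatic, too low when it is mainly in the gut.

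The size cannot be fixed from the documents. On the stated assumptions it runs from none (Fg = Fh = 1), through a negligible Fa excess at Fh = 0.9 and r = 0.05, to an Fa of about 1.15 at Fh = 0.5 and r = 0.25. For a true Fg of 0.5 with Fh = 1, Fa is reported at roughly half to six tenths of its true value over the same range of r.

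**What to change.** In SAP Table 4:

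1. Relabel the Fg row as the fraction escaping gut metabolism.
2. Report Fa × Fg = F/(1 - Eh) per participant alongside Fg and Fa. The product needs no metabolite-load assumption.
3. Present the separate Fg and Fa as conditional on a stated assumption, namely that hepatic first pass does not contribute to ML(po) - ML(iv), and flag any Fa above 1.
4. Correct the Eh rows in the same edit, because the product depends on them. Divide hepatic plasma clearance by Cb/Cp to obtain blood clearance, and make the Eh note divide by Qh, as the main formula does.

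Fg and Fa remain reported as the protocol specifies, so the primary endpoint list does not change. The cost is an SAP text edit, one extra derived column, and a more cautious reading of two primary components. No new samples or participants are needed.
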